Appendix 1. Schedule of Assessments

Visit	Screening ^a	Baseline/ Day1 ^c	END OF WEEK ^b																Every 12 Weeks	30 Day Follow- up		
			2	4	8	12	16	20	24	30	36	42	48/ ESDD ^d	50	52	56	60	64			72	
Visit Window	-30 days	0	±3	±3	±3	±3	±3	±3	±3	±3	±3	±3	±3	±3	±3	±3	±3	±3	±3	±5	±5	
Written Informed Consent	X																					
Medical History	X																					
Smoking Status	X	X		X	X	X	X	X	X	X	X	X	X	X	X		X	X	X	X		
Complete Physical Exam	X	X				X			X				X									
Symptom-Directed Physical Exam ^e			X	X	X		X	X		X	X	X		X	X	X	X	X	X	X		X
Serum Pregnancy Test ^f	X																					
Urine Pregnancy test ^f		X	X	X	X	X	X	X	X	X	X	X	X	X	X	X	X	X	X	X	X	
Serum FSH ^f	X																					
NIH cGVHD Diagnosis and Staging Criteria	X																					
NIH cGVHD Activity Assessment (NCAA) Form A with spirometry ^g		X		X	X	X	X	X	X	X	X	X	X			X	X	X	X	X		
NIH cGVHD Activity Assessment (NCAA) Form B ^h		X		X	X	X	X	X	X	X	X	X	X			X	X	X	X	X		
Lee Symptom Scale (LSS) ^h		X		X	X	X	X	X	X	X	X	X	X			X	X	X	X	X		

Visit	Screening ^a	Baseline/ Day1 ^c	END OF WEEK ^b																Every 12 Weeks	30 Day Follow- up	
			2	4	8	12	16	20	24	30	36	42	48/ ESDD ^d	50	52	56	60	64			72
Visit Window	-30 days	0	±3	±3	±3	±3	±3	±3	±3	±3	±5	±5	±5	±5	±3	±3	±3	±3	±3	±5	±5
Primary disease assessment per institutional guidelines	X								X				X								
Height	X																				
Vital Signs & Weight ^t	X	X	X	X	X	X	X	X	X	X	X	X	X	X	X	X	X	X	X	X	X
Hematology ^j	X	X	X	X	X	X	X	X	X	X	X	X	X	X	X	X	X	X	X	X	X
Chemistry ^k	X	X	X	X	X	X	X	X	X	X	X	X	X	X	X	X	X	X	X	X	X
Urine Analysis ^l	X	X	X	X	X	X	X	X	X	X	X	X	X	X	X	X	X	X	X	X	X
Metabolic Panel	X	X	X	X	X	X	X	X	X	X	X	X	X	X	X	X	X	X	X	X	X
HIV-1, HBV, & HCV Serology ^m	X																				
12 lead ECG-performed supine	X								X				X								
PK ⁿ			X	X	X	X	X	X	X	X	X	X	X				X		X		
Monitoring of calcineurin inhibitors and MPA ^o		X	X											X							
Biomarkers ^p	X	X	X	X	X	X	X	X	X	X	X	X	X	X	X	X	X	X	X	X	X
PFT ^s	X								X				X								
Randomize		X																			
Drug Dispensing ^q		X		X	X	X	X	X	X		X		X		X	X	X		X		
Written Informed Consent for OLE													X								

Visit	Screening ^a	Baseline/ Day1 ^c	END OF WEEK ^b																Every 12 Weeks	30 Day Follow- up		
			2	4	8	12	16	20	24	30	36	42	48/ ESDD ^d	50	52	56	60	64			72	
Visit Window	-30 days	0	±3	±3	±3	±3	±3	±3	±3	±3	±3	±3	±3	±3	±3	±3	±3	±3	±3	±5	±5	
Adverse Events	X	X	X	X	X	X	X	X	X	X	X	X	X	X	X	X	X	X	X	X	X	X
Concomitant Medications ^f	X	X	X	X	X	X	X	X	X	X	X	X	X	X	X	X	X	X	X	X	X	X

- 1) Evaluations to be completed within 30 days prior to Day 1.
- 2) All study visits are to be scheduled relative to the Day 1 visit date.
- 3) Initiation of treatment with the study drug must take place within 24 hours after the Baseline/Day 1 Visit
- 4) Early Study Drug Discontinuation visit to occur within 72 hours of last dose of study drug
- 5) Symptom-directed physical exam as needed
- 6) FSH: For female subject post-menopausal for less than two years, if FSH < 40 mIU/ mL a serum pregnancy test will be required. Women determined to be of child bearing potential will have a serum pregnancy test performed at screening. All subsequent visits will have a urine test, and positive urine pregnancy tests will be confirmed with a serum test. During OLE, urine pregnancy test will be performed every 4 weeks starting with end of visit Week 64.
- 7) NCAA Form A ([Appendix 3](#))
- 8)) with spirometry measures will be completed by the Investigator or Sub-I. In the OLE this will be assessed at Weeks 56, 60, 64, 72 and every 12 weeks thereafter. NCAA should also be performed at the time of initiation of second-line therapy.
- 9) LSS ([Appendix 4](#)) and the NCAA Form B ([Appendix 3](#)) is to be completed by the subject. The subject is to read the questionnaire by himself/herself and write/mark answers directly onto the questionnaire. In the OLE this will be assessed at Weeks 56, 60, 64, 72 and 96. The LSS and the NCAA Form B should also be administered at the time of initiation of second-line therapy.
- 10) Vital sign measurements include blood pressure, pulse, respiration rate, weight and temperature
- 11) Complete blood count (CBC) with differential platelet count
- 12) Chemistry profile: alkaline phosphatase, AST, ALT, GGT, total bilirubin, direct and indirect bilirubin, total protein, albumin, LDH, CPK, bicarbonate, BUN, calcium, chloride, creatinine, glucose, phosphorous, magnesium, potassium, sodium, uric acid, and amylase and (reflex lipase testing is performed in subjects with total amylase > 1.5 ULN)
- 13) Urine collection for urinalysis and urine pregnancy test (if applicable)
- 14) Subjects with positive HCV antibody and without detectable HCV RNA are permitted to enroll
- 15) Randomly timed PK sampling. Sites should enter the time of the last dose of study medication in the eCRF for sample reconciliation. PK samples will be drawn at Week 60 and every 12 weeks in the OLE.
- 16) For subjects receiving tacrolimus, cyclosporine or MMF the blood levels of tacrolimus, cyclosporine or the active metabolite of MMF (MPA) will be monitored at baseline/Day 1 (prior to starting ENTO or PTM), on day 2 or day 3 and day 6 or day 7 after initiating ENTO or PTM, and at the end of Week 2 and Week 50 study visit. Beyond these time points, concentration monitoring for tacrolimus, cyclosporine and MPA should follow the treating institutions protocol and therapeutic range for monitoring these medicines
- 17) Assessments may include but are not limited to: cytokines, cell subset analysis, pathway markers, and/or other B-cell activating factor, B-cell function, immunoglobulin levels, and/or antigen-specific B cell response. Timepoints may differ depending on the specific biomarker and will be outlined in the Central Lab Manual.
- 18) At visit 2, 30, 42 and (OLE visit 50) drug accountability only, study drug will not be dispensed at these visits
- 19) Will include the following: systemic corticosteroid dose, other immunosuppressive, antimicrobials, PPI
- 19) PFTs will include spirometry with bronchodilator, and diffusing capacity of the lungs for carbon monoxide (DLCO). PFTs will be done at ESDD, if ESDD visit greater than 12 weeks from Baseline. Any PFT done within 30 days prior to randomization can be used in lieu of Screening PFT.

Appendix 2. For Baseline + Subsequent Visits: Response Determination for the NIH cGVHD Activity Assessment (NCAA)

Organ	Complete Response	Partial Response	Progression
Skin	NIH Skin Score 0 after previous involvement	Decrease in NIH Skin Score by 1 or more points	Increase in NIH Skin Score by 1 or more points, except 0 to 1
Eyes	NIH Eye Score 0 after previous involvement	Decrease in NIH Eye Score by 1 or more points	Increase in NIH Eye Score by 1 or more points, except 0 to 1
Mouth	NIH Modified OMRS 0 after previous involvement	Decrease in NIH Modified OMRS of 2 or more points	Increase in NIH Modified OMRS of 2 or more points
Esophagus	NIH Esophagus Score 0 after previous involvement	Decrease in NIH Esophagus Score by 1 or more points	Increase in NIH Esophagus Score by 1 or more points, except 0 to 1
Upper GI	NIH Upper GI Score 0 after previous involvement	Decrease in NIH Upper GI Score by 1 or more points	Increase in NIH Upper GI Score by 1 or more points, except 0 to 1
Lower GI	NIH Lower GI Score 0 after previous involvement	Decrease in NIH Lower GI Score by 1 or more points	Increase in NIH Lower GI Score by 1 or more points, except from 0 to 1
Liver	Normal ALT, alkaline phosphatase, and Total bilirubin after previous elevation of 1 or more	Decrease by 50%	Increase by 2 × ULN
Lungs	- Normal %FEV1 after previous involvement - If PFTs not available, NIH Lung Symptom Score 0 after previous involvement	- Increase by 10% predicted absolute value of %FEV1 - If PFTs not available, decrease in NIH Lung Symptom Score by 1 or more points	- Decrease by 10% predicted absolute value of %FEV1 - If PFTs not available, increase in NIH Lung Symptom Score by 1 or more points, except 0 to 1
Joints and fascia	Both NIH Joint and Fascia Score 0 and P-ROM score 25 after previous involvement by at least 1 measure	Decrease in NIH Joint and Fascia Score by 1 or more points or increase in P-ROM score by 1 point for any site	Increase in NIH Joint and Fascia Score by 1 or more points or decrease in P-ROM score by 1 point for any site
Global	Clinician overall severity score 0	Clinician overall severity score decreases by 2 or more points on a 0-10 scale	Clinician overall severity score increases by 2 or more points on a 0-10 scale

ULN indicates upper limit of normal.

Appendix 3. For Baseline + Subsequent Visits: Chronic GVHD Activity Assessment- Clinician

FORM A

[figure not shown]
Current Patient Weight: _____ Today's Date: _____ MR#/Name: _____

CHRONIC GVHD ACTIVITY ASSESSMENT- CLINICIAN

Health Care Provider Global Ratings: 0=none 1= mild 2=moderate 3=severe	Where would you rate the severity of this patient's chronic GvHD symptoms on the following scale, where 0 is cGVHD symptoms that are not at all severe and 10 is the most severe cGVHD symptoms possible: 
 0 1 2 3 4 5 6 7 8 9 10 
 
 cGVHD symptoms not at all severe Most severe cGVHD symptoms possible 
	Since the last assessment would you say that this patient's cGVHD is +3= Very much better +2= Moderately better +1= A little better 0= About the same -1=A little worse -2=Moderately worse -3=Very much worse		
Mouth	Erythema None 0	Mild erythema or moderate erythema (<25%) 1	Moderate (≥25%) or Severe erythema (<25%) 2	Severe erythema (≥25%) 3
	Lichenoid None 0	Lichen-like changes (<25%) 1	Lichen-like changes (25-50%) 2	Lichen-like changes (>50%) 3
	Ulcers None 0		Ulcers involving (≤20%) 3	Severe ulcerations (>20%) 6
	Total score for all mucosal changes			
Gastrointestinal-Esophageal 
 • Dysphagia OR Odynophagia 	0= no esophageal symptoms 1=Occasional dysphagia or odynophagia with solid food or pills during the past week 2=Intermittent dysphagia or odynophagia with solid foods or pills, but not for liquids or soft foods, during the past week 3=Dysphagia or odynophagia for almost all oral intake, on almost every day of the past week			
Gastrointestinal-Upper GI 
 • Early satiety OR Anorexia OR Nausea & Vomiting 	0= no symptoms 1=mild, occasional symptoms, with little reduction in oral intake during the past week 2=moderate, intermittent symptoms, with some reduction in oral intake during the past week 3=more severe or persistent symptoms throughout the day, with marked reduction in oral intake, on almost every day of the past week			
Gastrointestinal-Lower GI 
 • Diarrhea 	0= no loose or liquid stools during the past week 1= occasional loose or liquid stools, on some days during the past week 2=intermittent loose or liquid stools throughout the day, on almost every day of the past week, without requiring intervention to prevent or correct volume depletion 3=voluminous diarrhea on almost every day of the past week, requiring intervention to prevent or correct volume depletion			

Lungs (Liters and % predicted) • Bronchiolitis Obliterans	FEV1	FVC	Single Breath DLCO (adjusted for hemoglobin)		TLC	RV
Liver Values	Total serum bilirubin mg/dL	ULN mg/dL	ALT U/L	ULN U/L	Alkaline Phosphatase U/L	ULN U/L
Baseline Values	Total Distance Walked in 2 or 6 Mins: 6 min  2 min 		Karnofsky or Lansky	Platelet Count K/uL	Total WBC K/uL	Eosinophils %
 Abnormality present but explained entirely by non-GVHD documented cause (specify site/alternate cause): _____  Abnormality present but explained entirely by non-GVHD documented cause (specify site/alternate cause): _____  Abnormality present but explained entirely by non-GVHD documented cause (specify site/alternate cause): _____						

	SCORE 0	SCORE 1	SCORE 2	SCORE 3
EYES	 No symptoms symptoms	 Mild dry eye symptoms not affecting ADL (requirement of lubricant eye drops \leq 3 x per day)	 Moderate dry eye symptoms partially affecting ADL (requiring lubricant eye drops > 3 x per day or punctal plugs), WITHOUT new vision impairment due to KCS	 Severe dry eye symptoms significantly affecting ADL (special eyewear to relieve pain) OR unable to work because of ocular symptoms OR loss of vision due to KCS
 Abnormality present but explained entirely by non-GVHD documented cause (specify): _____				
LUNGS	 No symptoms	 Mild symptoms (shortness of breath after climbing one flight of steps)	 Moderate symptoms (shortness of breath after walking on flat ground)	 Severe symptoms (shortness of breath at rest; requiring O ₂)
 Abnormality present but explained entirely by non-GVHD documented cause (specify): _____				
JOINTS AND FASCIA	 No symptoms	 Mild tightness of arms or legs, normal or mild decreased range of motion (ROM) AND not affecting ADL	 Tightness of arms or legs OR joint contractures, erythema thought due to fasciitis, moderate decrease ROM AND mild to moderate limitation of ADL	 Contractures WITH significant decrease of ROM AND significant limitation of ADL (unable to tie shoes, button shirts, dress self etc.)
 Abnormality present but explained entirely by non-GVHD documented cause (specify): _____				

Shoulder	1 (Worst)	2	3	4	5	6	7 (Normal)	 Not done
								
Elbow	1 (Worst)	2	3	4	5	6	7 (Normal)	 Not done
								
Wrist/finger	1 (Worst)	2	3	4	5	6	7 (Normal)	 Not done
								
Ankle	1 (Worst)	2	3	4 (Normal)				 Not done
								

FORM B

TODAY'S DATE: _____

MR#/NAME: _____

CHRONIC GVHD ACTIVITY ASSESSMENT-PATIENT SELF REPORT

Symptoms													
Please rate how severe the following symptoms have been in the last seven days . Please fill in the circle below from 0 (symptom has not been present) to 10 (the symptom was as bad as you can imagine it could be) for each item.	Not Present											As Bad As You Can Imagine	
	0	1	2	3	4	5	6	7	8	9	10		
Your skin itching at its WORST?	○	○	○	○	○	○	○	○	○	○	○	○	○
Your skin and/or joint tightening at their WORST?	○	○	○	○	○	○	○	○	○	○	○	○	○
Your mouth sensitivity at its WORST?	○	○	○	○	○	○	○	○	○	○	○	○	○
Your genital discomfort at its WORST? (Women – vagina, vulva, or labia) (Men – penis)	○	○	○	○	○	○	○	○	○	○	○	○	○
Eyes	What is your main complaint with regard to your eyes?												
	Please rate how severe this symptom is, from 0 (not at all severe) to 10 (most severe):						0 1 2 3 4 5 6 7 8 9 10						

Patient Global Ratings:

1. Overall, do you think that your chronic graft versus host disease is mild, moderate or severe?

1= mild
2=moderate
3=severe

2. Please circle the number indicating how severe your chronic graft versus host disease symptoms are, where 0 is cGvHD symptoms that are not at all severe and 10 is the most severe chronic GvHD symptoms possible.

0 1 2 3 4 5 6 7 8 9 10

cGvHD symptoms
not at all severe

Most severe cGvHD
symptoms possible

3. Compared to a month ago, overall would you say that your cGvHD symptoms are:

+3= Very much better
+2= Moderately better
+1=A little better
0= About the same
-1=A little worse
-2=Moderately worse
-3=Very much worse

Appendix 4. For Baseline + Subsequent Visits: Lee Symptom Scale

By circling one (1) number per line, please indicate how much you have been bothered by the following problems in the past 7 days:

SKIN:	Not at all	Slightly	Moderately	Quite a bit	Extremely
1. Abnormal skin color.....	0	1	2	3	4
2. Rashes.....	0	1	2	3	4
3. Thickened skin.....	0	1	2	3	4
4. Sores on skin.....	0	1	2	3	4
5. Itchy skin.....	0	1	2	3	4

EYES AND MOUTH:	Not at all	Slightly	Moderately	Quite a bit	Extremely
6. Dry eyes.....	0	1	2	3	4
7. Need to use eye drops frequently..	0	1	2	3	4
8. Difficulty seeing clearly.....	0	1	2	3	4
9. Need to avoid certain foods due to mouth pain.....	0	1	2	3	4
10. Ulcers in mouth.....	0	1	2	3	4
11. Receiving nutrition from an intravenous line or feeding tube....	0	1	2	3	4

BREATHING:	Not at all	Slightly	Moderately	Quite a bit	Extremely
12. Frequent cough.....	0	1	2	3	4
13. Colored sputum.....	0	1	2	3	4
14. Shortness of breath with exercise..	0	1	2	3	4
15. Shortness of breath at rest.....	0	1	2	3	4
16. Need to use oxygen.....	0	1	2	3	4

EATING AND DIGESTION:	Not at all	Slightly	Moderately	Quite a bit	Extremely
17. Difficulty swallowing solid foods....	0	1	2	3	4
18. Difficulty swallowing liquids.....	0	1	2	3	4
19. Vomiting.....	0	1	2	3	4
20. Weight loss.....	0	1	2	3	4

MUSCLES AND JOINTS:	Not at all	Slightly	Moderately	Quite a bit	Extremely
21. Joint and muscle aches.....	0	1	2	3	4
22. Limited joint movement.....	0	1	2	3	4
23. Muscle cramps.....	0	1	2	3	4
24. Weak muscles.....	0	1	2	3	4

ENERGY:	Not at all	Slightly	Moderately	Quite a bit	Extremely
25. Loss of energy.....	0	1	2	3	4
26. Need to sleep more/take naps.....	0	1	2	3	4
27. Fevers.....	0	1	2	3	4

MENTAL AND EMOTIONAL:	Not at all	Slightly	Moderately	Quite a bit	Extremely
28. Depression.....	0	1	2	3	4
29. Anxiety.....	0	1	2	3	4
30. Difficulty sleeping.....	0	1	2	3	4

Summary of the Lee Symptom Scale

Which 2 of the following organs/systems have you found to affect you the most in the last seven days:

- 1) Skin
- 2) Eyes
- 3) Mouth
- 4) Breathing
- 5) Eating and Digestion
- 6) Muscles and Joints
- 7) Energy
- 8) Mental and Emotional

Appendix 5. Predictive Probability of Success Calculation

Notation

Let

- n_1 =number of patients in treatment group
- n_0 =number of patients in control group
- n_{i1} =number of patients who stayed in trial at least 24 weeks or who stayed less than 24 weeks but responded already at interim in treatment group
- n_{i0} =number of patients who stayed in trial at least 24 weeks or who stayed less than 24 weeks but responded already at interim in control group
- n_{i11} =number of responders at interim in treatment group
- n_{i01} =number of responders at interim in control group
- x_1 =number of new responders after interim and at week 24 analysis in treatment group
- x_0 =number of new responders after interim and at week 24 analysis in control group

Predictive probability of success

Predictive probability of success is defined as the probability of obtaining a statistically significant 30% difference favorable result at the week 24 analysis (at 2-sided alpha level α), accounting for uncertainty about the true treatment effect given the data observed at the interim, and assuming that future data is subject to sampling variation given any possible true effect.

Predictive probability of success can be calculated as:

$$\sum_{x_1=0}^{n_1-n_{i1}} \sum_{x_0=0}^{n_0-n_{i0}} \left(\frac{n_{i11}+x_1}{n_1} > \left(\frac{n_{i01}+x_0}{n_0} + 0.3 \right) \right) \{pvalue(x_1, x_0) < 0.05\} f(n_1 - n_{i1}, x_1, n_{i11} + 1, n_{i1} - n_{i11} + 1) f(n_0 - n_{i0}, x_0, n_{i01} + 1, n_{i0} - n_{i01} + 1)$$

where function f is the probability density function of Beta-Binomial Distribution

$$f(n, x, a, b) = \binom{n}{x} \frac{\Gamma(x+a)\Gamma(n-x+b)}{\Gamma(n+a+b)} \frac{\Gamma(a+b)}{\Gamma(a)\Gamma(b)} \text{ where } \Gamma \text{ is gamma function.}$$

For Programming

```
/* **** */
/* Predictive probability of success Macro:
*/
/* Calculates the probability of statistical significance at final      */
/* analysis given data observed at interim                          */
/* **** */
/* Input Parameters:                                               */
/* n1 = sample size in treatment group                             */
/* n0 = sample size in control group                               */
/* ni1 = sample size stayed at least 24 weeks or less than 24 weeks but */
/*      responded at interim in treatment group                   */
/* ni0 = sample size stayed at least 24 weeks or less than 24 weeks but */
/*      responded at interim in control group                     */
/* ni11 = responders at interim in treatment group                */
/* ni01 = responders at interim in control group                  */
/* alpha = 2-sided alpha level at week 24 analysis                */
/* **** */
```

```
%macro PP_calc(n1,n0,ni1,ni0,ni11,ni01,alpha);
```

```
proc iml;
n1=&n1; /*sample size in treatment group*/
n0=&n0; /*sample size in control group*/
ni1=&ni1; /*sample size stayed at least 24 weeks or less than 24 weeks but
responded at interim in treatment group*/
ni0=&ni0; /*sample size stayed at least 24 weeks or less than 24 weeks but
responded at interim in control group*/
ni11=&ni11; /*responders at interim in treatment group*/
ni01=&ni01; /*responders at interim in control group*/

c1=(n1-ni1); /*rest patients who are potential to have week 24 responses in
treatment group*/
a1=ni11+1;
b1=ni1-ni11+1;
c0=(n0-ni0); /*rest patients who are potential to have week 24 responses in
treatment group*/
a0=ni01+1;
b0=ni0-ni01+1;

pm=j(c1+1,c0+1,0);
fd=j(4*(c1+1)*(c0+1),4,0); /*data output for fisher's exact test*/
do x1=0 to c1;
    p1=comb(c1,x1)*beta(x1+a1,c1-x1+b1)/beta(a1,b1); /*the probability to
observe x1 more responders in treatment group*/
    do x0=0 to c0;
        pass=(x1*(c0+1)+x0)*4;

        p0=comb(c0,x0)*beta(x0+a0,c0-x0+b0)/beta(a0,b0); /*the probability to
observe x0 more responders in control group*/
```

```
        pm=p1*p0; /*the probability to observe x1 more responders in
treatment group and x0 more responders in control group*/
        fd[(pass+1):(pass+4),2]=repeat(pm,4,1);

        fd[(pass+1),1]=ni11+x1; /*count of treatment responses at final*/
        fd[(pass+2),1]=n1-ni11-x1; /*count of treatment non-responses at
final*/
        fd[(pass+3),1]=ni01+x0; /*count of control responses at final*/
        fd[(pass+4),1]=n0-ni01-x0; /*count of control non-responses at
final*/

        su=((ni11+x1)/n1>(ni01+x0)/n0+0.3); /*marker if treatment is superial
30%*/
        fd[(pass+1):(pass+4),3]=repeat(su,4,1);

        rn=x1*(c0+1)+x0+1; /*replicate number*/
        fd[(pass+1):(pass+4),4]=repeat(rn,4,1);
    end;
end;

indicator=repeat(t({1 1 0 0, 1 0 1 0}), (c1+1)*(c0+1), 1);

fm=fd||indicator;
varNames={"count" "pm" "su" "rep" "group" "response"};
create mydata from fm [colname=varNames];
append from fm;
close mydata;

quit;

proc sort data=mydata;
by rep;
run;
proc freq data=mydata;
by rep;
tables group*response/exact cmh;
weight count;
ods output FishersExact=fx; /*output fisher's exact test result*/
run;
data fx1;
set fx;
if Name1='XP2_FISH';
keep rep Nvalue1;
run;

proc sort data=fx1;
by rep;
run;

data mydata1;
merge mydata fx1;
by rep;
if first.rep;
fp=(Nvalue1<&alpha)*pm*su; /*if the fisher's exact test is significant and
treatment is superial*/
```

```
drop count group response;  
run;
```

```
proc means data=mydata1 sum; /*add the probability together*/  
var fp;  
run;
```

```
%mend;
```

```
/* Sample macro call */
```

```
%PP_calc(n1=50,n0=50,ni1=25,ni0=25,ni11=20,ni01=10,alpha=0.05);
```

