2.2. Interim Analysis

The DMC is primarily responsible for reviewing safety data. Efficacy data will be reviewed only during the formal interim futility analysis after approximately 50% of subjects have been on study for 24 weeks, or have discontinued the study before 24 weeks, or have achieved a response prior to reaching 24 weeks. A non-binding futility rule will be implemented which is based on the predictive probability of success.

The predictive probability of success is defined as the probability of achieving statistical significance (two sided p-value < 0.05) and a $\geq 30\%$ difference in the BORR between the ENTO and placebo group at the study completion given the data observed at the interim.

If the predictive probability of success is $> 30\%$, the study will continue. If the predictive probability of success is $\leq 30\%$, the totality of the data including the DOR, response rate at Week 24, and safety data will be reviewed by the DMC to make a thorough risk-benefit assessment. The VP of Clinical Research and the VP of Biometrics at Gilead may review the interim futility analysis results to make subsequent decisions based on the DMC recommendations.

A 2-sided alpha of 0.001 will be allocated to this interim futility analysis; following the Haybittle-Peto approach, the week 24 analysis alpha level will be 0.05 (2-sided).

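### The SAP defines futility success as a difference of at least 30 points, but its formula and macro require more than 30, so the programmed predictive probability is not the defined one

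*SAP*

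**What the plan says.** SAP 2.2 defines success for the interim futility calculation as a two-sided p-value below 0.05 "and a $\geq 30\%$ difference in the BORR between the ENTO and placebo group at the study completion". A difference of exactly 30 points therefore counts. The result is set against a threshold: "If the predictive probability of success is $> 30\%$, the study will continue". At 30% or below, the DMC reviews the totality of the data. The rule is stated to be non-binding.

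Appendix 5 restates success as "the probability of obtaining a statistically significant 30% difference favorable result at the week 24 analysis", which does not settle the boundary. The displayed formula does settle it: the final ENTO rate must be strictly greater than the control rate plus 0.3. The macro follows the formula with "su=((ni11+x1)/n1>(ni01+x0)/n0+0.3" and multiplies that indicator by the Fisher result in "fp=(Nvalue1<&alpha)*pm*su". The only worked call is "PP_calc(n1=50,n0=50,ni1=25,ni0=25,ni11=20,ni01=10,alpha=0.05", which takes the planned 50 per arm from SAP 1.3.

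**The concern.** The text includes the 30-point boundary, while the formula and code exclude it. With two arms of 50 the boundary is an attainable result, because 0.30 × 50 = 15 responders. It is also the effect on which the trial was sized: 80% v 50% is 40 v 25 responders.

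There is a second fault in the code. It adds 0.3 to one decimal quotient and compares the sum with another. Such values are generally not exact in binary, so whether a tie passes can depend on rounding error in the last bit.

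At stake is a decision statistic. If outcomes that the SAP calls success are scored as failures, the predictive probability is understated and leans toward the branch at or below 30%. SAP 2.3 says the sponsor ended the study for lack of efficacy on the interim futility results, so the number should be the one that was defined.

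**Working it through.** **The plan's own figure.** SAP 1.3 states 75% power with 40 per arm, 50% v 80%, Fisher's exact test, two-sided 0.05. Exact enumeration of the two binomials gives 74.9%, so that figure reproduces. The documents report no value of the predictive probability itself.

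**Inputs.** 50 per arm (SAP 1.3); alpha 0.05, 25 per arm at interim, 20 v 10 responders (sample call, Appendix 5); threshold 30% (SAP 2.2).

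**Formula.** In each arm, the number x of new responders among the c subjects still to be evaluated is beta-binomial:

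f(c, x, a, b) = C(c, x) · B(x + a, c − x + b) / B(a, b), where a = interim responders + 1 and b = interim non-responders + 1.

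In the sample call, c = 25 in both arms, (a, b) = (21, 6) for ENTO and (11, 16) for placebo. The predictive probability sums the product of the two f terms over final outcomes with Fisher p < 0.05 that also meet the 30-point condition. That condition was coded three ways: at least 0.3 in exact fractions (SAP 2.2), more than 0.3 in exact fractions (Appendix 5 formula), and the macro line in double precision.

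**Step 1: the tied outcomes.** With 50 per arm, ties run from 15 v 0 to 50 v 35, which is 36 outcomes. The largest Fisher p among them is 0.0048, so the inequality alone decides them.

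| Rule | Ties counted as success |
|---|---|
| SAP 2.2 text | 36 of 36 |
| Appendix 5 formula | 0 of 36 |
| Macro, double precision | 7 of 36 |

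The seven are 17v2, 23v8, 33v18, 34v19, 44v29, 45v30 and 46v31. The design's own 40 v 25 is not among them.

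**Step 2: predictive probability, 25 per arm at interim.**

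| Interim responders | Text (≥) | Formula (>) | Macro |
|---|---|---|---|
| 20 v 10 (sample call) | 0.859 | 0.805 | 0.810 |
| 20 v 13 | 0.417 | 0.331 | 0.336 |
| 17 v 10 | 0.424 | 0.341 | 0.366 |
| 25 v 17 (largest gap) | 0.593 | 0.478 | 0.481 |

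In the sample call the ties carry 0.8587 − 0.8053 = 0.0534 of probability, and the macro recovers 0.8097 − 0.8053 = 0.0044 of it. Over all 26 × 26 = 676 interim outcomes, the gap between text and macro runs from 0 to 11.1 points, averages 1.1, and exceeds 5 points in 66.

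**Step 3: does the 30% flag change?**

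| Evaluated at interim (ENTO/placebo) | Outcomes where text and macro disagree | Example (text v macro) |
|---|---|---|
| 25/25 | 2 of 676 | only 7 v 0 and 25 v 18 |
| 26/24 | 9 | 20/26 v 12/24: 0.378 v 0.2995 |
| 24/26 | 8 | 11/24 v 5/26: 0.361 v 0.295 |

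At 25/25 the two affected outcomes are extreme. With slightly unequal counts, some affected outcomes have ordinary response rates.

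**Step 4: when the gap vanishes.** A tie at arm sizes n1 and n0 needs 10(a·n0 − b·n1) = 3·n1·n0, with a and b the final responder counts. At 49/51 the right side is 3 × 49 × 51 = 7,497, which is not a multiple of 10. No tie exists and all versions agree.

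**The case against.** **Nothing can now change.** The study has been terminated (SAP 2.3) and SAP 3.5 says no formal comparisons will be done. Correcting the code does not alter an interim already run. That stands as a limit on consequence, but the SAP still documents a decision statistic that its own code does not compute.

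**The rule is soft.** It is non-binding, and a value at or below 30% leads to a review of duration of response, Week 24 response and safety, not to an automatic stop. It is a futility rule, so the tie handling does not inflate type I error. This stands.

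**The text may be the slip.** Formula and macro agree on strict inequality, so the ≥ in SAP 2.2 could be the error. The documents do not establish intent. What is certain is that the two must agree.

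**Exact 50/50 is not assured.** The protocol plans approximately 100 subjects, and without ties the issue disappears. This stands as a condition, although 50/50 is the plan and the sample call.

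**The rounding part is secondary.** The count of 7 was obtained in double precision outside SAS. If SAS resolved ties exactly, the macro would match the strict formula (0 of 36) and the sample call would be 0.805, further from the definition.

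A reader might infer that the interim result was understated by some fixed amount, or that the trial was wrongly stopped. The documents support neither: they give no interim counts and no predictive probability, and the gap depends on the outcome. The opposite inference, that the flag is practically immune, holds only for exactly 25/25. The interim set in SAP 3.1.1 depends on follow-up, discontinuation or early response, so equal counts are not guaranteed.

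**Conclusion.** The inconsistency is real and can be checked from the SAP alone. Where the final arm sizes permit an exact 0.30 difference, as the planned 50 per arm do, the programmed predictive probability is at or below the one defined in SAP 2.2. The difference is 5 points in the SAP's own example and between 0 and about 11 points across interim outcomes at 25/25. It seldom moves the 30% flag, but with slightly unequal interim counts it can do so at ordinary response rates.

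The figures assume 50 per arm at the end and the Appendix 5 beta-binomial model; the macro figures also assume raw double-precision comparison. No effect on the actual decision is claimed. This is a minor correction, worth making because the statistic was the formal futility measure.

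**What to change.** Use one inequality in SAP 2.2, the Appendix 5 formula and the macro. To match the definition in SAP 2.2, change > to ≥ in the formula and replace the macro line with an integer comparison, for example:

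`su=(10*((ni11+x1)*n0-(ni01+x0)*n1) >= 3*n1*n0);`

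Check at 40 v 25 with 50 per arm: 10 × (40 × 50 − 25 × 50) = 7,500 and 3 × 50 × 50 = 7,500, so the tie passes as defined. If strict inequality was intended, amend SAP 2.2 instead and keep the integer form with >, so that rounding no longer decides ties.

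Then re-run the macro with the actual interim counts and state in the CSR whether the flag at or below 30% is unchanged. SAP 1 already provides for documenting changes made after finalization there. The cost is one symbol, one line of code, one re-run and a sentence in the CSR.
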